1 PROTOCOL SUMMARY

1.1 SYNOPSIS

Protocol title:

Open-label study of tusamitamab ravtansine (SAR408701) in combination with ramucirumab in participants previously treated for advanced gastric or gastroesophageal junction (GEJ) adenocarcinoma with CEACAM5-positive tumors

Brief title: Tusamitamab ravtansine (SAR408701) in combination with ramucirumab in pretreated participants with gastric cancer

Rationale:

Tusamitamab ravtansine monotherapy shows a significant level of activity and a favorable safety profile in heavily pretreated participants with metastatic nonsquamous, non-small-cell lung cancer (NSQ NSCLC) expressing carcinoembryonic antigen-related cell adhesion molecule 5 (CEACAM5; 1). In participants with gastric cancer (GC) in the main dose escalation part of first-in-human (FIH) study TED13751, 1 partial response (PR) was observed. In the GC FIH expansion cohort, participants received tusamitamab ravtansine as monotherapy at 100 mg/m² administered every 2 weeks (Q2W); in total, 16 participants were treated, and no objective response was reported. Stable disease (SD) was reported for 37.5% of the participants enrolled from this heavily pretreated (median of 3 prior treatments) participant population; 81.3% of these participants had prior taxane therapy. In the FIH “loading dose” escalation cohort, 2 participants with GC were treated at the recommended dosing regimen (170 mg/m² then 100 mg/m² Q2W): a single participant who had been overdosed with twice the loading dose had a nonconfirmed PR, the other participant had SD.

Ramucirumab (a monoclonal antibody antagonist of vascular endothelial growth factor receptor 2 [VEGFR2]) combined with the antitubulin agent paclitaxel provides improved efficacy as compared to single-agent paclitaxel as second-line therapy for GC. This combination therapy was approved as second-line treatment based on the results of the Phase 3 RAINBOW study (2).

Synergy of tusamitamab ravtansine (containing the cytotoxic antitubulin agent DM4) activity in combination with ramucirumab may lead to improved efficacy in treating GC patients with a high unmet need; further the combination of tusamitamab ravtansine and ramucirumab may have a better safety profile compared to the combination of paclitaxel with ramucirumab. Nonclinical evaluations of the combination of tusamitamab ravtansine with a VEGFR2 antagonist were performed in mice with GC patient-derived xenografts (PDXs) to evaluate the substitution of tusamitamab ravtansine for paclitaxel in the combination with ramucirumab. Improved efficacy, optimized treatment duration, and a favorable safety profile were observed for combinations of tusamitamab ravtansine with an anti-VEGFR2 agent as compared to combinations of paclitaxel with an anti-VEGFR2 agent. The positive data from this work support replacing paclitaxel with tusamitamab ravtansine in combination with ramucirumab in a clinical study. Combining ramucirumab with tusamitamab ravtansine rather than with paclitaxel may lead to improved efficacy with a favorable safety profile of the combination in participants with GC.

Objectives and endpoints

Objectives	Endpoints
Primary	

Part 1: to confirm the recommended tusamitamab ravtansine loading dose Q2W when given in combination with ramucirumab in advanced gastric or gastroesophageal junction (GEJ) adenocarcinoma populationPart 2: To assess the antitumor activity of tusamitamab ravtansine loading dose Q2W in combination with ramucirumab in advanced gastric or GEJ adenocarcinoma	
Part 1: Incidence of study drug related dose-limiting toxicities (DLTs) at Cycle 1 and Cycle 2 (C1D1 to C2D14)Part 2: Objective Response Rate (ORR), defined as the proportion of participants with confirmed complete response (CR) or partial response (PR) as best overall response (BOR) per Response Evaluation Criteria in Solid Tumors (RECIST) 1.1
Secondary	

To assess the safety and tolerability of tusamitamab ravtansine loading dose Q2W in combination with ramucirumabTo assess the durability of the response to treatment with tusamitamab ravtansine loading dose Q2W in combination with ramucirumabTo assess progression-free survival (PFS) of tusamitamab ravtansine loading dose Q2W in combination with ramucirumabTo assess the disease control rate (DCR) of tusamitamab ravtansine loading dose Q2W in combination with ramucirumabTo assess the pharmacokinetics (PK) of tusamitamab ravtansine loading dose Q2W and ramucirumab when given in combinationTo assess the immunogenicity of tusamitamab ravtansine loading dose Q2W when given in combination with ramucirumab	
Incidence of treatment-emergent adverse events (TEAEs), serious adverse events (SAEs), and laboratory abnormalities according to the National Cancer Institute (NCI) Common Terminology Criteria for Adverse Events (CTCAE) V5.0Duration of response (DOR), defined as the time from first documented evidence of CR or PR until progressive disease (PD) determined per RECIST 1.1 or death from any cause, whichever occurs firstProgression-free survival, defined as the time from the first investigational medicinal product (IMP) administration to the date of the first documented disease progression or death due to any cause, whichever comes firstDisease control rate, defined as the proportion of participants with confirmed CR or PR or SD as BOR per RECIST 1.1Pharmacokinetic parameters of tusamitamab ravtansine and ramucirumabIncidence of antitherapeutic antibodies (ATAs) against tusamitamab ravtansine

Overall design:

Brief summary:

This is a single group, treatment, Phase 2, open-label, single-arm study to confirm the recommended dose (RD), safety, PK, and preliminary antitumor activity of tusamitamab ravtansine combined with ramucirumab in participants previously treated for gastric or gastroesophageal adenocarcinoma with CEACAM5-positive (defined as CEACAM5 immunohistochemical [IHC] intensity $\geq 2+$ in $\geq 50\%$ of cells) tumors.

This will be a 2-part study.

Part 1 (safety run-in):

In Part 1, participants will receive ramucirumab 8 mg/kg followed by tusamitamab ravtansine at 170 mg/m² (150 mg/m²) at Day 1 Cycle 1, and ramucirumab 8 mg/kg followed by tusamitamab ravtansine 100 mg/m² at Cycle 2 and Q2W in all subsequent cycles. In the case that it is decided to reduce the initial loading dose of tusamitamab ravtansine to DL-1 (Table 1), a tusamitamab ravtansine loading dose of 150 mg/m² will be administered to participants on Day 1 of Cycle 1.

Table 1 - Dose levels for Part 1 (safety run-in)

[figure not shown]
Dose level (DL)	Tusamitamab ravtansine	Ramucirumab
Starting dose	170 mg/m ² Q2W Cycle 1; 100 mg/m ² Q2W Cycle 2 and thereafter	8 mg/kg Q2W
Minus -1 (DL -1)	150 mg/m ² Q2W Cycle 1; 100 mg/m ² Q2W Cycle 2 and thereafter	8 mg/kg Q2W

BSA = body surface area; DL -1=dose level -1; Q2W = every 2 weeks.

Infusion of tusamitamab ravtansine will be administered at least 1 hour after the end of ramucirumab infusion for at least the first 2 cycles. For participants with a BSA >2.2 m², the tusamitamab ravtansine dose will be calculated based on a BSA of 2.2 m².

As no overlap in the safety profiles for ramucirumab and tusamitamab ravtansine is anticipated, the starting dose for tusamitamab ravtansine is selected as the maximum tolerated dose (MTD) used in studies evaluating tusamitamab ravtansine as loading-dose monotherapy. Enough participants will be enrolled in Part 1 to achieve 6 to 12 participants evaluable for DLTs to confirm the recommended dose. The tolerability of the combination is assessed in Part 1 according to the algorithm illustrated in Figure 1. The DLT observation period is the first 2 cycles (approximately 28 days). A DLT-evaluable participant must have completed 2 cycles of treatment or have been discontinued from study treatment because of a DLT; DLT-nonevaluable participants will be replaced. A minimum delay of 1 week is required between the initial dose in the first participant treated in a DL cohort and dosing of the next 2 participants treated at the same DL.

Figure 4 Decision tree for tusamitamab ravtansine leading dose in Part 1

Note: Abbreviations: DL -1 = dose level -1 (150 mg/m²); DLT = dose-limiting toxicity.
In case of 2 or more DLTs at DL-1, an alternative dosage may be considered or the study may be stopped.

In Part 2 of the study, the recommended dose confirmed in Part 1 will be evaluated for activity in 26 additional participants. A total of 32 participants, including participants treated at the recommended dose in Part 1, will be evaluated for activity.

Number of participants:

Approximately 158 participants will be prescreened to achieve up to approximately 38 treated participants, based on an estimated CEACAM5 prescreening failure rate of 70% and an estimated study screening failure rate of 20%.

Intervention groups and duration:

The duration of the study for a participant will include:

- **Screening period:** up to 28 days.
- **Treatment period:** once successfully screened, enrolled participants may receive study intervention until disease progression, unacceptable adverse event (AE), death, initiation of a new anticancer therapy, or the participant's or investigator's decision to stop the treatment. Each cycle of treatment will have a duration of 2 weeks. After discontinuing study intervention, participants will return to the study site approximately 30 days after the last investigational medicinal product (IMP) administration or before the participant receives another anti-cancer therapy, whichever is earlier, for end-of-treatment assessments.
- **Safety follow-up visit:** will be performed approximately 90 days after the last dose of IMP. If any ongoing related AE/SAE is resolved or stabilized, no further follow-up visit is needed.

Participants who stopped treatment before documented progressive disease (PD; ie, achieving SD or CR or PR) should undergo a tumor assessment and an on-site follow-up visit every 8 weeks (± 7 days) after the last tumor assessment until radiological disease progression, start of a new anticancer therapy, death, withdrawal of a participant's consent, or cut-off date for secondary efficacy endpoints, whichever comes first. After PD or a start of new anticancer therapy, a participant will be followed until any ongoing related AE/AESI/SAE is resolved or stabilized.

The study cut-off for analysis of the primary endpoint, ORR, corresponds to the date on which all evaluable treated participants have had at least 2 postbaseline tumor assessments, experienced confirmed objective response, or have discontinued the study for any reason. This study cut-off can be up to approximately 16 weeks (12 weeks for 2 tumor assessments and 4 weeks for confirmation of response, if needed) after the last participant's first IMP administration.

The final study cut-off date for analysis of the secondary efficacy endpoints, which include DOR and PFS, will be 4 months after the cut-off date for the primary analysis. At that time, the primary analysis of ORR and DCR will also be updated.

After the cut-off date for the analysis of secondary efficacy endpoints, participants still receiving study treatment can continue study treatment, if clinical benefit is observed, until PD, unacceptable toxicity, initiation of a new anticancer therapy, or withdrawal of participants' consent, and will continue to undergo all assessments as per the study flow chart.

The expected duration of study intervention for participants may vary, based on disease progression date; median expected duration of study per participant is estimated as 34 weeks (up to 4 weeks for screening, a median of 18 weeks for treatment, and a median of 12 weeks for end-of-treatment assessments and the safety follow-up visit).

Study interventions

Study interventions include tusamitamab ravtansine and ramucirumab. To prevent hypersensitivity reactions, each administration will be preceded by premedication.

Administration of tusamitamab ravtansine will be initiated after the completion of ramucirumab infusion. As infusion-related reactions (IRRs) may occur during or following ramucirumab administration, a 1 hour observation period following the ramucirumab infusion is mandatory prior to the initiation of tusamitamab ravtansine administration for the first 2 infusions. If the patient shows no evidence of an IRR with the first 2 infusions of ramucirumab, no observation period is required for subsequent infusions. In the event an IRR occurs thereafter, the 1 hour observation should be reinstated.

Each cycle of treatment will have a duration of 2 weeks.

Investigational medicinal products

Ramucirumab

Ramucirumab will be administered prior to administration of tusamitamab ravtansine.

- Formulation: CYRAMZA[®] (ramucirumab) is a concentrate for solution for infusion supplied in 10 mL or 50 mL single-use vial. Each vial contains either 100 mg ramucirumab in 10 mL (10 mg/mL) or 500 mg ramucirumab in 50 mL (10 mg/mL).
- Route of administration: IV infusion
- Dose regimen: Ramucirumab will be administered as an 8 mg/kg IV infusion administered over 1 hour on Day 1 of every 2 week cycle.

Tusamitamab ravtansine

- Formulation: tusamitamab ravtansine is supplied as a 25 mL extractable volume of concentrate for solution for infusion of 125 mg contained in a 30 mL Type I glass vial.
- Route of administration: intravenous (IV) infusion.
- Dose regimen: tusamitamab ravtansine loading dose at 170 mg/m² (or RD) will be administered via IV infusion over 1 hour 30 minutes on Day 1 of Cycle 1, followed by 100 mg/m² Q2W from Cycle 2 and in all other cycles.
- For participants with a body surface area (BSA) >2.2 m², the dose will be calculated based on a BSA of 2.2 m².

Noninvestigational medicinal products

Both tusamitamab ravtansine and ramucirumab have potential risk for IRR; therefore, premedication with an IV histamine H1 antagonist (diphenhydramine 50 mg IV or equivalent; eg, cetirizine, promethazine, dexchlorpheniramine, according to local approval and availability) given approximately at least 15 minutes before ramucirumab administration is required for all participants. If a participant previously experienced an IRR following a dose of ramucirumab or tusamitamab ravtansine, premedication for subsequent infusions will also include dexamethasone 10 mg IV and acetaminophen (paracetamol). All drugs used as premedication will be entered on the concomitant premedication page.

Posttrial access to study medication:

Not applicable.

Statistical considerations:

- **Analysis of primary endpoint:**
 - Incidence of DLTs during the DLT observation period (Cycle 1 and Cycle 2) will be summarized on the DLT-evaluable population, by DL (if applicable).

- Objective response rate (ORR) will be summarized on the all-treated population using descriptive statistics and 95% exact confidence intervals (CIs) will be provided using the Clopper-Pearson method. As a supplementary analysis, ORR will also be summarized on the activity population.
- **Analysis of secondary efficacy endpoints:**
 - Duration of response will be summarized for the subgroup of participants who achieve confirmed objective response on the all-treated population with descriptive statistics using Kaplan-Meier methods. The median DOR and associated 95% CI will be provided.
 - Progression-free survival will be summarized on the all-treated population using Kaplan-Meier methods. The median PFS times and associated 95% CI will be provided, along with probabilities of being progression-free at different time points.
 - Disease control rate will be summarized on the all-treated population using descriptive statistics and 95% CIs will be provided using the Clopper-Pearson method. As a supplementary analysis, DCR will also be summarized on the activity population.
- **Analysis of safety endpoints:**
 - Number and percentage of participants experiencing TEAEs by primary system organ class (SOC) and preferred term will be summarized by NCI-CTCAE V5.0 Grade (all grades, and Grade ≥ 3) on the all-treated population. Similar summaries will be prepared for TEAEs related to IMP, TEAEs leading to permanent full/partial intervention discontinuation, TEAEs leading to dose modification or dose interruption, serious TEAEs, TEAEs with fatal outcome, adverse events of special interest (AESIs), and AEs/SAEs occurring during the posttreatment period. In addition, the number (%) of participants with any Grade 5 AE (TEAE and posttreatment) will be summarized.
 - Hematology and clinical chemistry results will be graded according to the NCI-CTCAE V5.0, when applicable. Number and percentage of participants with laboratory abnormalities (all grades and by grade) using the worst grade during the on-treatment period will be provided on the all-treated population.

Data Monitoring/Other committee: Yes

[figure not shown]
Study Committee (SC; Part 1)

The SC includes the Investigators or designees and Sponsor team members and, when appropriate, ad hoc experts. The SC will have regular meetings every 2 weeks during Part 1 (safety run-in phase) of the study.

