Administration of the study treatment will be discontinued in the event of a TEAE that persists despite appropriate dose modifications or any other AE that, in the opinion of the Investigator, warrants discontinuation.

Ramucirumab or tusamitamab ravtansine can be discontinued prematurely. The patient will remain on study treatment until the last IMP can be discontinued for disease progression, unacceptable AE, or the participant's or investigator's decision to stop the treatment. The reason for premature discontinuation will be captured in the appropriate eCRF page.

Dose modifications different from those stated in the protocol should be made only in consultation with the Sponsor unless required for immediate participant safety.

All changes to study treatment administration must be recorded in the eCRF.

In the event of neutropenia or febrile neutropenia, therapeutic G-CSF should be administered according to the current American Society of Clinical Oncology (ASCO) guidelines ([13](#)); for specific recommendations for this study, refer to Appendix 6 ([Section 10.6](#)).

The acceptable treatment window for tusamitamab ravtansine and ramucirumab administration is ± 2 days.

See Appendix 6 in [Section 10.6](#) for further guidance for dose modification or discontinuation. Approved product labels for ramucirumab should be followed for supportive care and dose modification requirement due AEs not listed in [Section 10.6](#). During the conduct of the study, a second dose reduction may be needed; such an action must be decided in a case-by-case discussion with the Sponsor. In case a dose reduction is necessary for Cycle 2 and subsequent cycles, the study intervention will be administered as follows in [Table 7](#).

Table 7 - Dose modification for toxicity

Drug name	Dose	1 st dose reduction ^a	2 nd dose reduction ^a
tusamitamab ravtansine	100 mg/m ² Q2W	80 mg/m ² Q2W	(not permitted)
ramucirumab	8 mg/kg Q2W	6 mg/kg Q2W	5 mg/kg Q2W

^a Dose modification is applicable from Cycle 2. At Cycle 1 the dose will remain the recommended dose (170 mg/m² or 150 mg/m²).

Any participant who requires a tusamitamab ravtansine or ramucirumab dose reduction will continue to receive a reduced dose until discontinuation from tusamitamab ravtansine/ramucirumab or discontinuation from the study.

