9.2 POPULATIONS FOR ANALYSES

The following populations for analyses are defined in [Table 9](#):

Table 9 - Populations for analyses

Population	Description
Prescreened	All participants who signed the prescreening informed consent for CEACAM5 assessment of their biopsy.
Screened	All participants who signed screening informed consent for study participation.
Enrolled	Participants from screened population who have been allocated to intervention regardless of whether the intervention was received or not.
All-treated	All enrolled participants exposed to the study treatment, regardless of the amount of treatment administered. This population is the primary population for all efficacy parameters.
DLT-Evaluable (Part1)	All enrolled participants who received 2 cycles with at least 80% of the intended dose for both tusamitamab ravtansine and ramucirumab at each of the first 2 infusions unless they discontinued the study intervention before the end of Cycle 2 due to a DLT.
Activity	All treated participants who have measurable disease at study entry and at least 1 postbaseline evaluable tumor assessment. Participants with no postbaseline evaluable tumor assessment but with an early clinical progression or who died from disease progression will also be included in this set. This population is the secondary population for all efficacy parameters.
PK	All participants from the all-treated population with at least 1 postbaseline PK concentration (whatever the cycle and even if dosing is incomplete) with adequate documentation of dosing and sampling dates and times.
ATA	All participants from the all-treated population with at least 1 postbaseline ATA result (negative, positive or inconclusive).

Abbreviations: ATA = antitherapeutic antibody; CEACAM5 = carcinoembryonic antigen-related cell adhesion molecule 5; DLT = dose-limiting toxicity; PK = pharmacokinetic.

Participants exposed to study intervention before or without being enrolled will not be considered enrolled and will not be included in any analysis population. The safety experience of these participants will be reported separately.

Enrolled participants for whom it is unclear whether they took the study intervention will be considered as exposed and will be included in the safety population.

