Ocular toxicity (continued)	Grade 3 Symptomatic with marked decrease in visual acuity (best corrected visual acuity worse than 20/40 or more than 3 lines of decreased vision from known baseline, up to 20/200); corneal ulcer; limiting selfcare activity of daily life	Administer ramucirumab at same dose, and same day as tusamitamab ravtansine or administer ramucirumab as planned if definitive discontinuation of tusamitamab ravtansine	1 st episode: Omit tusamitamab ravtansine until resolution (asymptomatic), and restart tusamitamab ravtansine with dose reduction. 2 nd episode: definitive discontinuation of tusamitamab ravtansine.	Standard ocular examination weekly until resolution ^{c, d} Start curative treatment per ophthalmologist recommendation. After resuming study treatment, participant should be followed with standard ocular examination by every 2 cycles, e en asymptomatic during next four cycles. If no recurrence, standard process with follow-up with ocular symptom is resumed Management of study drug upon recurrence to be discussed according to Grade of the event at recurrence, clinical benefit from study drug and recommendation from the ophthalmologist
	Grade 4 Perforation or best corrected visual acuity of 20/200 or worse in the affected eye.	Administer ramucirumab as planned.	Definitive discontinuation of tusamitamab ravtansine.	Complete the corneal examination as recommended by ophthalmologist. Repeat the standard ocular examination weekly ^c until resolution ^d . Start curative treatment per ophthalmologist recommendation.
Conduction disorder associated with tusamitamab ravtansine	Grade 1 Mild symptoms	Administer ramucirumab as planned.	tusamitamab ravtansine administration to be continued upon decision by the Investigator and Sponsor, depending on the nature of the conduction disorder.	ECG performed once weekly until event resolution. Additional evaluations such as LVEF and Holter monitoring should be performed when relevant.
	Grade ≥2	Administer ramucirumab as planned.	Definitive discontinuation of tusamitamab ravtansine.	ECG to be repeated twice weekly until event resolution. Prompt cardiology consultation Additional evaluations such LVEF and Holter monitoring should be performed when relevant.

Event	Symptoms severity (Nadir) (NCI CTCAE v5)	Management of IMP dosing (ramucirumab)	Management of IMP dosing (tusamitamab ravtansine)	Supportive care guidelines

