# 2 ANALYSIS POPULATIONS

The following populations for analyses are defined:

Population	Description		
Prescreened	All participants who signed the prescreening informed consent for CEACAM5 assessment of their biopsy.		
Screened	All participants who signed the screening informed consent for study participation.		
Enrolled	Participants from screened population who have been allocated to intervention regardless of whether the intervention was received or not.		
All-treated	All enrolled participants exposed to the study treatment, regardless of the amount of treatment administered. All safety analyses will be performed on this population, which is also the primary population for analysis of all efficacy parameters.		
DLT-evaluable (Part 1)	All enrolled participants who received 2 cycles with at least 80% of the intended dose for both tusamitamab ravtansine and ramucirumab at each of the first 2 infusions. Any participant who experienced a DLT during that period will also be DLT-evaluable.		
Activity	All-treated participants who have measurable disease at study entry and at least 1 postbaseline evaluable tumor assessment. Participants with no postbaseline evaluable tumor assessment but with an early clinical progression or who died from disease progression will also be included in this set. This population is the secondary population for analysis of efficacy parameters.		
Pharmacokinetic (PK)	All participants from the all-treated population with at least 1 postbaseline PK concentration (whatever the cycle and even if dosing is incomplete) with adequate documentation of dosing and sampling dates and times.		
ATA	All participants from the all-treated population with at least 1 postbaseline ATA result (negative, positive, or inconclusive).		
Population without trial impact	All treated participants:		
(disruption) due to COVID-19	
 
without any critical or major deviation related to COVID-19
 
		
	
 
and who did not permanently discontinue treatment due to COVID-19
 
		
	
 
and who did not permanently discontinue study due to COVID-19.
 
		

Table 4 - Populations	for analyses
-----------------------	--------------

In practice, a participant will be included in the enrolled population if the question "Will the subject continue in the treatment phase?" has been answered "Yes" in the "Completion of screening phase" e-CRF page.

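### Under the protocol, a Cycle 1 DLT that stops only one drug, or leaves Cycle 2 ungiven, can be classed non-evaluable and replaced, although the SAP would count it

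*Protocol*

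**What the plan says.** The DLT-evaluable set is defined in three places in the protocol. The synopsis (1.1) and Overall Design (4.1) use the same sentence: "A DLT-evaluable participant must have completed 2 cycles of treatment or have been discontinued from study treatment because of a DLT". The synopsis adds that "DLT-nonevaluable participants will be replaced", and 4.1 says the same. Table 9 in Section 9.2 is stricter on the first route: "All enrolled participants who received 2 cycles with at least 80% of the intended dose for both tusamitamab ravtansine and ramucirumab". That threshold applies separately to the first and the second infusion. Its only exception for a DLT is "unless they discontinued the study intervention before the end of Cycle 2 due to a DLT".

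Section 6.5 says what happens when one of the two drugs is stopped early: "The patient will remain on study treatment until the last IMP can be discontinued". It also allows the other drug to continue until progression.

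Appendix 6 (Section 10.6) sets the dosing response to toxicity. For a first Grade 3 keratopathy it reads: "Omit tusamitamab ravtansine until resolution (asymptomatic), and restart tusamitamab ravtansine with dose reduction". For Grade 4 keratopathy and Grade 4 peripheral neuropathy, tusamitamab ravtansine is stopped and ramucirumab goes on. For Grade 4 hypertension the reverse applies. For Grade 3 or 4 hemorrhage both drugs stop.

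The SAP (Section 2, Table 4) keeps the 80% requirement but adds: "Any participant who experienced a DLT during that period will also be DLT-evaluable". Its text after the table also admits a DLT that occurs before the end of the window and is validated by the Study Committee. It excludes anyone overdosed by at least 30% at either of the first two infusions. The SAP version history records the changed definition.

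**The concern.** DLT incidence is the Part 1 primary endpoint and the basis for confirming the loading dose. The usual principle is that a participant who had the event counts, and only participants who left early without the event are replaced. The protocol ties the DLT exception to discontinuation rather than to the event. Its own management table often does not discontinue all treatment after a DLT. Where the two do not meet, a participant with a confirmed DLT could be swapped for a new one. That error runs in one direction, toward a lower observed DLT rate, in a run-in of only 6 to 12 evaluable participants.

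**Working it through.** **Step 1. Sort the possible courses after a DLT.** The two-cycle route is read with Table 9. The discontinuation route is read with Section 6.5, so treatment is discontinued only when the last drug stops.

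| Course | Two-cycle route | Discontinuation route | Protocol | SAP Table 4 |
|---|---|---|---|---|
| A. DLT after both infusions at 80% or more, Cycle 2 completed | met | not needed | evaluable | evaluable |
| B. Cycle 1 DLT, delay, then both drugs given at 80% or more | met | not needed | evaluable | evaluable |
| C. Cycle 1 DLT, one drug stopped, the other continued | fails | fails | non-evaluable, replaced | evaluable |
| D. Cycle 1 DLT, Cycle 2 held and not given, treatment not stopped for the DLT | fails | fails | non-evaluable until Cycle 2 is given or all treatment stops for the DLT | evaluable |
| E. Both drugs stopped because of the DLT | fails | met | evaluable | evaluable |

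On the synopsis sentence alone, a participant in course C who takes one drug in Cycle 2 might be said to have completed two cycles. Table 9 closes that reading by requiring both drugs.

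**Step 2. Place the Appendix 6 rows.** Table 6 makes any Grade 4 non-hematologic event a DLT.

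- Course C: Grade 4 keratopathy, Grade 4 neuropathy, Grade 4 hypertension.
- Course B once Cycle 2 is given: first-episode Grade 4 neutropenia beyond 7 days and first-episode Grade 3 febrile neutropenia (both drugs resume at the same dose), and first-episode Grade 3 keratopathy (reduced tusamitamab ravtansine, ramucirumab unchanged).
- Course E: Grade 4 hemorrhage.

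Dose check from Table 7: a first tusamitamab ravtansine reduction is 80/100 = 80%, which just meets the threshold. A first ramucirumab reduction is 6/8 = 75%, which fails it if the intended dose means the full planned dose.

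**Step 3. Illustrate the size.** The documents give no operating characteristics for the run-in, so there is no stated figure to reproduce. Assumptions:

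- n = 6 evaluable participants, the lower end of the 6 to 12 in Section 9.1.
- Trigger of 2 or more DLTs. The text states this only for DL -1, and Figure 1 is not shown.
- True DLT risk p of 33%, or of 22%. Section 4.3 reports 2 DLTs in the first 6 evaluable participants at 170 mg/m² as monotherapy (2/6 = 33%), then none in 3 more (2/9 = 22%).
- A share f of DLT participants is replaced. The documents give no value.

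Among those who end up counted, the DLT risk is q = p(1 − f)/(1 − pf). The chance of reaching the trigger is 1 − (1 − q)^6 − 6q(1 − q)^5.

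| p | f = 0 | f = 0.25 | f = 0.50 |
|---|---|---|---|
| 0.33 | q = 0.330, 64% | q = 0.270, 51% | q = 0.198, 34% |
| 2/9 | q = 0.222, 40% | q = 0.176, 29% | q = 0.125, 17% |

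Worked cell, p = 0.33 and f = 0.25: q = 0.2475/0.9175 = 0.270, and the chance is 0.512.

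**The case against.** Four points can be made for the plan.

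First, a reader might infer that a DLT counts only when treatment is discontinued. The text does not say that. The quoted sentence has two routes, and completing two cycles is enough with or without a DLT. Much of Appendix 6 therefore does no harm. Section 4.3 also says that all DLTs in the main first-in-human escalation came at the end of Cycle 2, after both infusions. This stands, and it confines the problem to courses C and D.

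Second, a reader might infer that the Part 1 primary result will be biased. SAP Table 4 makes every participant with a DLT evaluable, so the reported endpoint is already corrected. This stands too. The SAP does not touch replacement, however, which is governed only by the protocol. The SAP was approved on 17-Jul-2023, about 20 months after the first enrollment on 21-Nov-2021, and the protocol's amendment history is given as not applicable.

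Third, discontinuation might be read to include temporary or partial discontinuation. Section 7.1 covers temporary stops, and both documents speak of full and partial discontinuation. The evaluability sentences do not say which is meant, and Section 6.5 supports the narrower sense for study treatment. This shows ambiguity but does not remove the conflict.

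Fourth, Section 6.5 refers to DLTs observed in participants, and Section 10.1.5.1 refers to appropriate data. Neither binds the Study Committee to the evaluable set, and DLTs are reported to the sponsor as events of special interest. It would go too far to say that the committee would disregard a confirmed DLT. The documents do not say which set it counts on, and that is what needs stating.

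**Conclusion.** The point holds in a limited form. On the written protocol, a Cycle 1 DLT followed by stopping one drug, or by a Cycle 2 infusion that is held and never given, can be non-evaluable and replaced. The SAP would count the same participant. The set behind replacement and dose confirmation can therefore differ from the set that is reported, and any difference runs toward missing toxicity.

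The documents do not support a claim that most DLTs are lost or that the reported Part 1 incidence is biased. The probabilities in the tables are illustrations. The replaced shares have no source, the trigger at the starting dose is assumed, and the 33% and 22% risks come from monotherapy. There the two DLTs were delays for Grade 2 keratopathy, an event that Table 6 here does not itself list. With 6 to 12 evaluable participants, a single replaced DLT could change the decision, so the wording is worth correcting.

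**What to change.** Align the synopsis (1.1), Section 4.1 and Table 9 with the SAP Table 4 wording: any participant with a confirmed DLT in the observation period is DLT-evaluable, whatever the later dosing, delay, or full or partial discontinuation. State that a participant with a confirmed DLT is not replaced. State that the Study Committee counts on this same set. Reconcile this with the SAP's exclusion of overdosed participants, which as written could remove a participant whom Table 4 includes because of a DLT.

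If the run-in has already closed, a listing of every replaced Part 1 participant with the reason would show whether the gap had any effect.

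The cost is wording in three protocol passages, plus a sentence each on replacement, committee counting and overdose. No dose or clinical management rule changes. The downside is that the observed DLT rate may be slightly less favourable.
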